- To compare the effect of RAGT by use of the Atalante self-balance exoskeleton with conventional Rehabilitation training (cRHB), for improving **static balance**, **dynamic balance**, mobility, and **self-perception of gait impairment** measured with:
 - **Static Balance** by the Berg Balance Scale (BBS), considering a clinically relevant change for improvement in balance as measured by BBS was +3 points, meaning that PwMS are likely to perceive that as a reproducible and clinically important change in them balance performance.¹⁷
 - **Dynamic balance** by the Timed Up and Go test (TUG)¹⁸
 - **Mobility** measured by modified Rivermead Mobility Index (mRMI)¹⁹

- **Self-perception of gait** impairment by Multiple Sclerosis Walking Scale-12 (MSWS-12)²⁰
- **Instrumented gait analysis** by the G-walk device (assessing gait cycle duration, step length, propulsion index, support phase percentage D/I, oscillation phase percentage D/I, double/unique support phase percentage).
- To compare the effect of RAGT by use of the Atalante self-balance exoskeleton with conventional Rehabilitation training (cRHB) on quality of life, emotional status and fatigue measured at pre and post-intervention with:
 - Multiple Sclerosis Quality of Life-54 (MSQoL 54 Health Survey Spanish version)²¹
 - Hospital Anxiety and Depression Scale (HADs) considering a clinically relevant change of 1.7 points at HADs²²
 - The Modified fatigue scale (MFIS) ^{23 24}
 - The patient' physical effort of each session by means of the scale of perception of the effort R.P.E of Borg at the end of each training^{25 26}.
 - To evaluate the epigenetic blueprint of rehabilitation training by comparing the genome wide chromatin accessibility of peripheral blood mononuclear cells (PBMCs) before and after RAGT or cRHB, by Assay for Transposase-Accessible Chromatin sequencing (ATACseq).
 - To test the hypothesis that genome wide chromatin accessibility compared to clinical measures can be useful for identifying molecular mechanisms underlying rehabilitation therapies.
 - To compare the changes induced by RAGT versus cRHB on the overall chromatin accessibility, and specific genome regions and pathways.
 - Use the biological samples to provide additional functional and mechanistic information about the rehabilitation effects and subject health, disease or state.

3 Materials And methods

3.1 Design:

This trial is a prospective, randomized, rater-blinded study (cRHB (N=30) vs RAGT (N=30)).

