For the control group, this protocol includes 24 one-hour sessions of cRHB training during 8 weeks three times per week, under the supervision of a qualified rehab team.

For the intervention group (RAGT) this protocol includes 24 one-hour sessions of RAGT during 8 weeks three times per week, under the supervision of a qualified rehab team.

Additionally, peripheral blood (6ml) will be taken from all subjects at three timepoints: at baseline (T1), after the 8 weeks of rehabilitation treatment (T2) and, if possible, one year after T4. Biological samples will then be given a unique identifier and transferred to researchers for analysis.

Informed consent will be obtained from patients prior to inclusion in the study, which will be carried out in accordance with the Declaration of Helsinki.

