3.3 Enrollment and Screening

Subjects will be evaluated for their eligibility from neurorehabilitation and neurology outpatient clinics at the Multiple Sclerosis Center of Catalonia (Cemcat).

Potential subjects will be referred to the study via Cemcat Physicians. A member of the research team will screen the referral and confirm they meet the necessary inclusion and exclusion criteria. Following confirmation of criteria, potential subjects will be contacted by phone to schedule an initial visit for consent and baseline assessment.

Additionally, peripheral blood (6ml) will also be taken from all subjects at baseline (T1).

Prior to all testing, each of the 60 selected participants will have time to read the consent form and ask questions (see Draft Informed Consent). The consent process will take place at the Multiple Sclerosis Centre of Catalonia (Cemcat, Vall d'Hebron Barcelona Hospital Campus, [name]).

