3.4 Assessments

The following information will be collected for all patients: age, sex, weight, height, type of MS, years from the diagnosis, Expanded Disability Status Scale (EDSS) and type of support device.

To ensure that training sessions are well tolerated, we will assess patients' blood pressure and heart rate weekly. We will also monitor the appearance of pain in any part of the body related to the RAGT at end of each training session using a pain registry (type of pain, location, intensity)²⁷.

3.4.1.1 To reduce the incidence of any type of muscle injury the physical therapist before each RAGT session will assess the level of spasticity using the Numeric Rating Scale measure of spasticity (NRS). The 0–10 NRS asks patients to indicate their level of spasticity on a scale of 0–10, where 0 is no spasticity and 10 is the worst possible spasticity. This type of rating tool is widely utilized in clinical settings to quickly assess pain.²⁸

A record of any unexpected Serious Adverse Events (SAE) within trial episodes will be kept. These are defined as death, a life-threatening adverse event or an event occurring as a result of the use of the device that requires medical intervention.

After the 8 weeks of rehabilitation treatment (T2) and, if possible, one year after T4, peripheral blood (6ml) will be taken from all subjects to perform the subsequent molecular analysis.

Molecular analysis

Peripheral blood mononuclear cells (PBMCs) will be purified using the Ficoll-Hypaque density gradient method according to manufacturer's instructions. Briefly, whole blood will be extracted by venepuncture and collected in CPT Vacutainer tubes (Becton Dickinson, BDAM362781) and centrifuged at 2250g for 25 min. Supernatant will then be collected, and washed twice with enriched saline (0.9% NaCl, 2%FBS). PMBC containing pellet will then be resuspended with 1 ml of complete media (RPMI1640 + 2% FBS) and cells will be counted and assessed for viability using a Countess 3 automated cell counter (Invitrogen). PBMCs will be adjusted to 5×10^6 cells/ml in freezing media media (90% FBS, 10% DMSO), and frozen at -80°C using a [name]™ Freezing Container (Thermo Scientific™) for 24 h and stored in liquid nitrogen vapor phase.

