Once all samples are collected, chromatin will be extracted from the frozen PBMCs. Briefly, each vial containing 5×10^6 cells will be thawed and centrifuged at 300g for 5 min at 4°C . The supernatant will then be removed, and cells will be mixed with 100 μL of lysis buffer (10 mM NaCl, 3 mM MgCl₂, 10 mM Tris-HCl pH7.4, 0.1% Tween-20, 0.1% NP40) and lysed on ice for 4 min. Followed by 2x1ml washes (10 mM NaCl, 3 mM MgCl₂, 10 mM Tris-HCl pH7.4, 0.1% Tween20) before centrifuging at 500g for 5 min at 4°C .

Next, ATAC-seq libraries will be generated according to manufacturer guidelines. Briefly, transposition mix (Illumina, Cat# 20031198) will be added to the nuclear pellets, incubated at 37°C for 30 min, and DNA purified using the QIAGEN MinElute PCR Purification Kit (QIAGEN, Cat#28004). DNA fragments will be amplified by PCR for 10 to 11 cycles and resulting libraries purified using the QIAGEN MinElute PCR Purification Kit. The libraries will then be sequenced with an Illumina Novaseq 6000 S4 flow cell using 150 bp paired-end reads (Illumina, Cat# 20027466). FASTQ files will be generated from the NovaSeq BCL outputs and used as input to the ENCODE ATAC-seq pipeline (<https://github.com/ENCODE-DCC/atac-seq-pipeline>) using the MACS2 peak-caller with all default parameters. Differential accessibility will be initially calculated between groups using the csaw package.

To identify differentially open chromatin regions between groups from ATAC-seq, the R package edgeR will be used to fit a generalized linear model (GLM) to test for the effect of rehabilitation between T0 and T1 samples. In addition to time group (T0 vs. T1), we will also compare the two different rehabilitation treatments (cRHB vs. RAGT at T1). We will also use surrogate variable analysis (SVA) to capture unknown sources of variation (e.g., batch effects, age, sex, library preparation, etc) statistically independent from time or treatment group assignments. SVA decomposes the variation that is not accounted for by known factors such as time group or treatment into orthogonal vectors that can then be used as additional covariates when fitting a model to test for differential accessibility or expression.

Benjamini-Hochberg P value correction will be used to select differentially open peaks at an FDR of 5%.

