Differentially open ATAC-seq peaks will then be annotated with regard to functional and positional information. HOMER will be used to annotate peaks based on the relative gene position (promoter (± 2 kb of known TSS), intergenic,

intronic, among others). For functional annotation of peaks, we will use a simplified version of the 18-state ChromHMM-derived chromatin states (such as TSSs, enhancers, repressed polycomb, transcriptionally active, or other states such as ZNFs or heterochromatin) obtained from Roadmap Epigenomics data for PBMC and T cell subsets.

For gene-based analyses, HOMER will be used to assign each differentially open ATAC-seq peak to the nearest TSS, as measured from the peak center. We will then assess enrichment using the hypergeometric test followed by Benjamini-Hochberg FDR adjustment for P values, as previously mentioned.

Further functional and ontological enrichment analyses will be performed using ClueGO and WikiPathways that will allow us to identify pathways among genes associated to differentially open peaks.

Finally, we will scan the data for transcription factor (TF) footprints using the PIQ algorithm which integrates genome-wide TF motifs with chromatin accessibility estimates profiled at base pair resolution to generate a list of possible footprint matches for a motif. In a nutshell, this will allow the identification of chromatin accessibility blueprint generated by the different rehabilitation therapies tested in this trial, as well as gather valuable data of its underlying molecular mechanisms that in turn might lead to the identification of novel therapeutic targets.

Type outcome	Test	Baseline (T1)			RAG Session 1-24 (S1-S24)			end of training (T2)			Follow up at 2 months (T3)			Follow up at 1 year (T4)		
		CRO	PROMs	Blood sample	CRO	PROMs	Blood sample	CRO	PROMs	Blood sample	CRO	PROMs	Blood sample	CRO	PROMs	Blood sample
Pain	1	Pain registry		x			x			x			x			
Physiologic indicators	2	Heart rate	x			x			x			x				
	3	Arterial pressure	x			x			x			x				
Effort	4	Rating perception exertion The Borg R.P.E scale				x										
Fatigue:	5	Modified fatigue scale (MFIS)		x						x						
Depression	6	Hospital Anxiety and Depression Scale (HADS)		x						x						
Health-related quality of life	7	MSQoL 54 Health Survey		x						x						
Mobility	8	Modified Rivermead Mobility Index	x						x			x				
Disability	9	Expanded Disability Status Scale (EDSS) de Kurtzke	x						x			x				

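### The ATAC-seq contrasts use time labels that conflict with the rest of the protocol, and on the likely pre/post reading they omit baseline from the arm estimate and name no participant term

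*Combined protocol and SAP*

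**What the plan says.** **Time points.** Section 3.1 schedules blood "at baseline (T1), after the 8 weeks of rehabilitation treatment (T2) and, if possible, one year after T4". Section 3.3 repeats that "peripheral blood (6ml) will also be taken from all subjects at baseline (T1". Section 3.4 places the second sample at T2: "After the 8 weeks of rehabilitation treatment (T2) and, if possible, one year after T4, peripheral blood (6ml) will be taken from all subjects". Table 1 has the same numbering, with T1 as baseline and a column headed "end of training (T2".

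**Aims.** Section 2.2 sets two aims that matter here. One is a before-after evaluation, "by comparing the genome wide chromatin accessibility of peripheral blood mononuclear cells (PBMCs) before and after RAGT or cRHB". The other is a comparison between arms: "To compare the changes induced by RAGT versus cRHB on the overall chromatin accessibility, and specific genome regions and pathways".

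**Model.** The molecular analysis text in section 3.4 fits an edgeR generalized linear model to "test for the effect of rehabilitation between T0 and T1 samples". It then continues: "In addition to time group (T0 vs. T1), we will also compare the two different rehabilitation treatments (cRHB vs. RAGT at T1". Surrogate variables are added for unknown sources of variation, with batch, age and sex among the examples. Peaks are selected by Benjamini-Hochberg at a 5% false discovery rate (FDR). No participant term, baseline covariate or arm-by-time term is named. Section 4 gives a matched-pairs Wilcoxon test for repeated measurements but does not connect it to the edgeR model.

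**The concern.** There are three gaps between the aims and the stated model.

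1. **Labels.** By the protocol's own definitions, the only between-arm contrast falls at baseline, and the before-after contrast uses a time point that does not exist elsewhere in the text.
2. **Arm contrast.** If the labels are read as pre and post, the arms are compared on the post-treatment sample alone. The aim is about changes, and baseline samples are to be taken from all subjects, but they do not contribute to the estimated arm effect.
3. **Before-after contrast.** The same people are sampled twice, but the model as described does not say that the two samples are linked.

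At stake is whether the contrasts can be run as written and how many truly changed peaks they can detect. The primary 10-MWT comparison is not touched.

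**Working it through.** The documents give no power or sample-size figure for ATAC-seq, so there is no stated figure to reproduce.

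**Step 1. Which reading is meant.** Sections 3.1, 3.3, 3.4 (blood sampling) and Table 1 agree on T1 = baseline and T2 = after 8 weeks. Only the molecular analysis text uses T0. It describes the T0-to-T1 comparison as the effect of rehabilitation, which makes sense only if treatment lies between the two. The probable meaning is therefore T0 = before and T1 = after, that is, T1 and T2 in the protocol's numbering.

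**Step 2. Precision on that reading.** From section 3.1, n = 30 per arm, so there are N = 60 before-after pairs if all are complete and the arms are pooled. Assume a standard deviation s for a peak at both times, and let rho be the correlation between one person's two samples. The documents give no rho, so a range is shown.

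- Arm contrast, post-only: variance 2s²/n
- Arm contrast, baseline-adjusted: 2s²(1 − rho²)/n
- Arm contrast, plain change: 4s²(1 − rho)/n
- Before-after, pairing ignored: computed as 2s²/N
- Before-after, paired: 2s²(1 − rho)/N

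| rho | adjusted / post-only, 1 − rho² | change / post-only, 2(1 − rho) | paired / unpaired, 1 − rho |
|---|---|---|---|
| 0 | 1.00 | 2.00 | 1.00 |
| 0.3 | 0.91 | 1.40 | 0.70 |
| 0.5 | 0.75 | 1.00 | 0.50 |
| 0.7 | 0.51 | 0.60 | 0.30 |

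A plain change contrast is less precise than post-only whenever rho is below 0.5. Baseline adjustment is never worse in this large-sample formula.

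For one peak at nominal two-sided 5% with an assumed 0.5 SD arm effect, the post-only standard error is √(2/30) = 0.258. Power is Φ(0.5/0.258 − 1.96), about 49%. Adjusted at rho 0.5, the standard error is √(2 × 0.75/30) = 0.224 and power is about 61%.

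**Step 3. Arm contrast under the 5% FDR (simulation).** Assumptions: 10,000 independent normal peaks, 10% truly changed, 0.8 SD effect, 30 versus 30, t-tests and ANCOVA in place of edgeR, no surrogate variables. Share of changed peaks found, approximate to a few points:

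| rho | post-only | baseline-adjusted | plain change |
|---|---|---|---|
| 0 | 48% | 46% | 6% |
| 0.3 | 48% | 54% | 23% |
| 0.5 | 48% | 70% | 49% |
| 0.7 | 48% | 91% | 85% |

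The direction does not depend on the 10%. At rho 0.3, 0.5 and 0.7:

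- with 1% of peaks changed, post-only finds 14–16%, against 18%, 34% and 70% adjusted;
- with 20% changed, post-only finds 60–61%, against 66%, 79% and 94% adjusted.

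**Step 4. Before-after contrast (simulation).** 60 people, assumed 0.5 SD shift, 10% of peaks changed, 5% FDR. The result depends on how much between-person variation the surrogate variables absorb. That was varied by letting none, half or all of the person variance come from five factors shared across peaks, with the number of factors taken as known.

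| rho | unpaired, none captured | unpaired, half shared | unpaired, all shared | paired |
|---|---|---|---|---|
| 0.3 | 27% | 42% | 60% | 56–57% |
| 0.5 | 21% | 56% | 82% | 81% |
| 0.7 | 6% | 76% | 98% | 98% |

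At rho 0, ignoring pairing finds 32% and pairing finds 29%. With a 0.7 SD shift even the none-captured gap narrows, to 86% versus 95%, 90% versus 99% and 95% versus 100% at rho 0.3, 0.5 and 0.7.

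The realised FDR with pairing ignored and nothing captured was 4.5%, 0.7%, below 0.1% and 0% at rho 0, 0.3, 0.5 and 0.7. It is therefore never above the planned 5%.

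**The case against.** The best defence is that this is a numbering slip in a secondary analysis. A competent analyst would read T0 and T1 as pre and post and would probably pair the samples anyway. Much of that stands, and it rules out several stronger readings that a reader might infer.

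- **That the plan intends to compare arms before treatment.** The labels say so literally, but the description of the T0-to-T1 test as a rehabilitation effect points the other way.
- **That the post-only arm contrast is biased.** It is not. The arms are randomised, and only precision and the match to the stated aim suffer.
- **That the baseline samples are wasted.** They drive the before-after contrast and, in a joint fit, would inform dispersion and surrogate variables. They are absent only from the arm-effect estimate.
- **That the plan has decided to ignore pairing.** The text is silent. It gives time group and treatment as examples of known factors, not as a full list, and section 4 shows that paired testing is familiar to the authors. Silence still leaves the model unspecified.
- **That most changed peaks will be missed.** Figures such as 6% versus 98% arise only if the surrogate variables capture no person-level variation. The plan's surrogate variables are a real safeguard, and if they captured all of that variation pairing would add nothing.
- **That false positives rise.** With positive correlation, ignoring pairing is conservative.

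What remains is that the labels are wrong as written, the participant link is unstated, and surrogate variables do not by themselves specify a paired design.

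**Conclusion.** The point holds as a matter of specification and efficiency, not validity. The label conflict is plain from the text. The schedule figure could not be seen, so T0 can only be said to be undefined in the written text.

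The size of the loss is conditional. For the arm contrast, baseline adjustment ranges from a loss of about 2 percentage points at rho 0 to a gain of about 43 at rho 0.7 (91% against 48%). For the before-after contrast, pairing gains nothing if the surrogate variables capture all person variation. With half shared it gains about 14, 25 and 22 points at rho 0.3, 0.5 and 0.7. In the worst case it gains 30, 60 and 92 points.

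These figures rest on assumed effect sizes, rho, share of changed peaks and factor structure, none of which the documents give, and on normal-theory tests, not an edgeR fit. The relabelling and the participant term are firm recommendations. Baseline adjustment of the arm contrast is an efficiency gain that also brings the analysis closer to the stated aim.

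**What to change.** In the molecular analysis text of section 3.4:

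1. Relabel the contrasts to the protocol's time points: T2 versus T1 for before-after, and cRHB versus RAGT at T2 for the arms.
2. Include participant as a blocking term in the T2 versus T1 model. Re-estimate the surrogate variables with participant among the known factors, because that term already absorbs stable characteristics such as sex and, over 8 weeks, age.
3. In a separate fit, adjust the T2 arm contrast for the same peak's T1 accessibility, or use a common baseline mean with participant as a random effect. The fit must be separate because a fixed participant term absorbs arm. Do not default to a plain change contrast.

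The 5% FDR can stay.

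**Cost.** No extra blood or sequencing is needed. Chromatin is to be extracted only once all samples are collected, so the text can be corrected before accessibility data exist. Item 1 is wording only. Item 2 fits the planned edgeR model, uses only participants with both samples, and loses about 3 points if rho is zero (29% against 32%). Item 3 loses about 1 to 2 points if rho is zero. Its peak-specific covariate or random effect may need a routine other than a single edgeR design matrix.

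### The bulk PBMC ATAC-seq analysis has no cell-composition term, and surrogate variables as described cannot remove a change in cell mix aligned with time or arm

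*Combined protocol and SAP*

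**What the plan says.** All references are to the combined protocol and SAP.

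- **Aim.** Section 2.2 (Secondary Aims) sets out to find the epigenetic blueprint of training by "comparing the genome wide chromatin accessibility of peripheral blood mononuclear cells (PBMCs) before and after RAGT or cRHB". It also aims to identify the molecular mechanisms behind the therapies.
- **Material.** Section 3.4 (Molecular analysis): "Peripheral blood mononuclear cells (PBMCs) will be purified using the Ficoll-Hypaque density gradient method". The cell measurement per sample is total number and viability: "cells will be counted and assessed for viability using a Countess 3 automated cell counter". After storage, "chromatin will be extracted from the frozen PBMCs", with no sorting step.
- **Model.** edgeR is used to "fit a generalized linear model (GLM) to test for the effect of rehabilitation between T0 and T1 samples". These labels appear to mean the baseline and end-of-training samples, which the rest of the protocol calls T1 and T2. The two arms are also compared at the later sample. Peaks are selected by Benjamini-Hochberg at a 5% false discovery rate.
- **Adjustment.** "We will also use surrogate variable analysis (SVA) to capture unknown sources of variation", with batch, age, sex and library preparation as examples. These sources are described as "statistically independent from time or treatment group assignments".
- **Use of the results.** Called peaks go on to functional annotation, pathway enrichment and transcription-factor footprinting. T-cell subsets appear only as reference chromatin states for annotating peaks already called; they are not a model term.

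**The concern.** PBMCs are a mixture of cell types, and many regulatory regions are open in some types and closed in others. Bulk accessibility at such a region moves if chromatin changes inside cells, or if the proportions of cells change. The plan has no measurement or model term that separates the two.

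Surrogate variables are the natural place to look for protection, but the plan describes them as unrelated to time and arm. Those are the two directions in which a shift in cell mix would do harm. Every region specific to the shifted cell type would move together, and the enrichment and footprint steps would tend to return that cell type's own programme under the name of a rehabilitation mechanism. False discovery control does not help, because the bulk difference is real; only its interpretation is wrong. Randomisation does not settle it for the arm contrast either, since the mix can change differently after allocation.

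The protocol's own background describes rehabilitation and exercise as acting on the immune system. The two explanations therefore need to be told apart, although that background does not show that proportions shift.

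**Working it through.** **1. Is composition handled anywhere?** Sections 2.2 and 3.1 to 3.4 and Table 1 contain no subset count, flow cytometry, sorting, deconvolution or composition covariate.

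**2. Can the surrogate variables as described remove an aligned shift?** Let X hold the time and arm terms and U the surrogate variables. If U is unrelated to the design in the sample, U'X = 0. Least squares then gives b = (X'X)⁻¹X'y whether or not U is in the model. The tested coefficient is unchanged; only the residual variance falls. This is exact for least squares and approximate for the edgeR model. Cell-mix variation unrelated to time or arm can be absorbed. The aligned part cannot.

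**3. How easily would a shift be detected?** The plan gives no figure to reproduce, so the inputs below are assumptions, except the 30 per arm (section 3.1).

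- Region open in one cell type only, no change per cell, share of PBMCs rising from 15%.
- Signal change d = log2(new share / 0.15).
- SD 0.3 or 0.5 log2 units, complete data, two-sided p<0.001.
- Under Benjamini-Hochberg at 5%, a cut-off of 0.001 applies when 2% of peaks are called (0.05 × 0.02 = 0.001). The real cut-off depends on the data.

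Within one arm, paired: non-centrality = d / (SD/√30), 29 df, critical t = 3.659.

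| New share | d | Non-centrality, SD 0.3 / 0.5 | Chance of p<0.001 |
|---|---|---|---|
| 16% | 0.093 | 1.70 / 1.02 | 4% / 1% |
| 17% | 0.181 | 3.30 / 1.98 | 38% / 7% |
| 18% | 0.263 | 4.80 / 2.88 | 86% / 25% |
| 20% | 0.415 | 7.58 / 4.55 | about 100% / 80% |

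Arm contrast, unpaired, 15% versus 18%: non-centrality = 0.263 / (SD × √(2/30)), 58 df, critical t = 3.466. For SD 0.3 this is 3.40, giving 48%. For SD 0.5 it is 2.04, giving 9%.

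**4. Simulation at 5% FDR.** This used a log-linear stand-in with no within-cell effect: 30 per arm, 4,000 peaks, 30% of them cell-type-specific, one cell type at 20% of PBMCs, a batch factor, and five runs per setting. All of these are assumptions except the arm size. Mean peaks called:

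| Contrast and shift | No surrogate variables | Orthogonal surrogate variables | Cell fraction as covariate |
|---|---|---|---|
| Time, 0 points | 0 | 50 | 0 |
| Time, 2 points | 1.4 | 8.4 | 0.2 |
| Time, 3 points | 3 | 20 | 0 |
| Time, 5 points | 85 | 154 | 0.2 |
| Arm, 2 points | 0 | 1.6 | 0 |
| Arm, 3 points | 0 | 1.2 | 0 |
| Arm, 5 points | 11 | 70 | 0.2 |

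Coefficients with and without the orthogonal variables agreed to about 1e-16, as step 2 requires. The counts need care. With no systematic shift, the orthogonal column still averaged 50, because one run of five gave 220. Chance alignment of a nuisance factor with visit is the likely cause. The last column contains no surrogate variables, so its like-for-like comparison is with the first (85 against 0.2). The simulation supports the direction of the argument, not a rate.

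**The case against.** **No shift is documented.** A reader might infer that a cell-mix change will be reported as a chromatin effect. The documents do not support that: nothing in them says rehabilitation moves PBMC proportions, or by how much. At one or two percentage points detection is often unlikely, and the randomised arm contrast is less sensitive than the paired one. This stands, and the point is conditional for that reason. The table also uses the most sensitive kind of region, and the plan does not state that its time contrast is paired.

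**The algorithm is not named.** An iteratively re-weighted form of SVA, whose vectors may correlate with time, removed nearly all false calls in the same simulation (0 to 0.2 peaks). That stands as a fact about the method. The plan's wording describes variables independent of time and arm, so it does not commit to that form.

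**A composition change is a real change in bulk PBMC accessibility.** This also stands. As a description of the PBMC pool the unadjusted result is valid; only the within-cell reading is at risk.

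**Therapy.** Disease-modifying therapy is missing from the listed characteristics ("age, sex, weight, height, type of MS, years from the diagnosis, Expanded Disability Status Scale (EDSS) and type of support device"), and a reader might call that a further error. The documents do not support this. Section 3.2.1 requires six months of stable therapy and section 3.2.2 excludes changes during the study. Therapy must therefore be known for eligibility and is meant to be constant between samples, and randomisation balances it in expectation between arms.

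**Conclusion.** The concern holds in conditional form. The analysis has no cell-composition term, and the surrogate variables as described cannot remove a cell-mix change aligned with time or arm. If such a shift occurs, composition-driven peaks could be presented as within-cell remodelling.

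Under the stated assumptions the chance of detecting such a region runs from 1% (15% to 16%, SD 0.5) to about 100% (15% to 20%, SD 0.3) in the paired contrast. For the arm contrast at 15% versus 18% it is 48% or 9%. These figures rest on assumed shares, SDs and cut-off, and none predicts what this trial will find.

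It would also go too far to say that a peak is epigenetic only if it survives adjustment. Cell mix is measured after randomisation and may lie on the path from training to chromatin, so adjustment can remove real effects. The matter concerns a secondary aim. It should be corrected, but it does not touch the primary outcome.

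**What to change.** Add a pre-specified sensitivity analysis to the Molecular analysis text of section 3.4:

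1. Estimate the main PBMC fractions per sample from the same ATAC-seq reads by reference-based deconvolution, naming the reference and the cell types in advance.
2. Report the fractions by time and arm.
3. Fit the edgeR model with and without the fractions as covariates, and report differential peaks from both.
4. Describe peaks that disappear on adjustment as compatible with a change in cell mix. Limit within-cell mechanistic wording, including pathways and footprints, to peaks seen in both analyses.
5. Name the SVA algorithm, and say whether its variables may correlate with time or arm.

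Therapy class can be an optional covariate in the arm contrast; nothing more is needed there.

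**Cost.** Bioinformatics time and a few degrees of freedom; no new blood or assay. Chromatin is extracted only after all samples are in, so the text can be settled before any sequencing data exist. The main drawback is that the fractions come from the reads being tested and may be mediators, so adjustment can absorb real effects. That is why both versions are shown and neither replaces the other.

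### For the cRHB vs RAGT chromatin contrast, recorded age and sex (and batch) are left to surrogate variables described as independent of treatment; if these are orthogonal to arm, the test is anti-conservative for peaks linked to those factors

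*Combined protocol and SAP*

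**What the plan says.** Section 3.1 sets the allocation: "This trial is a prospective, randomized, rater-blinded study (cRHB (N=30) vs RAGT (N=30" patients. No stratification by sex or age is stated. Section 3.4 lists what is recorded for every patient, including "age, sex, weight, height, type of MS, years from the diagnosis".

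The molecular analysis within section 3.4 names two edgeR contrasts. The first is to "test for the effect of rehabilitation between T0 and T1 samples". The second is between arms at one time point: "we will also compare the two different rehabilitation treatments (cRHB vs. RAGT at T1". The plan adds "surrogate variable analysis (SVA) to capture unknown sources of variation (e.g., batch effects, age, sex, library preparation, etc", and calls this variation "statistically independent from time or treatment group assignments". On construction it says that "SVA decomposes the variation that is not accounted for by known factors such as time group or treatment into orthogonal vectors", which then enter the model as extra covariates. Peaks are selected by Benjamini-Hochberg at an FDR of 5%.

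Time and treatment are the only known factors named. No explicit term for age, sex, batch, patient or arm-by-time is stated, and no algorithm for the surrogate variable analysis (SVA) is named.

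**The concern.** Age and sex are known, and processing batch is knowable to the laboratory, but the plan classes all three as unknown. A covariate orthogonal to arm cannot change the arm coefficient in a linear model; it only lowers the error variance. If the surrogates are built that way, they take sex, age or batch noise out of the denominator and leave the chance difference between arms in the numerator. The test then rejects too often for the peaks those factors drive.

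Comparing the two therapies on chromatin accessibility is a stated secondary aim (section 2.2). The selected peaks feed gene annotation and pathway enrichment, so peaks reflecting a sex or age imbalance would carry through to the mechanistic interpretation. The primary walking-speed comparison is not touched.

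**Working it through.** The documents give no sample size, power or expected peak count for the ATAC-seq analysis, so there is no figure of the plan's own to reproduce.

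**Inputs from the documents.** 30 per arm; age and sex recorded; surrogates independent of treatment; arm contrast at a single time point; FDR 5%.

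**Assumptions (not in the documents).** 50-75% women, i.e. 30 to 45 of 60; sex effect b of 1, 2, 3 or 5 residual SDs; a surrogate that recovers sex apart from its arm-related part; a Gaussian linear model in place of the edgeR GLM.

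**Step 1: chance imbalance.** By the hypergeometric distribution (30 drawn from 60), the arms differ by 6 or more women with probability 0.20 if there are 30 women and 0.07 if there are 45. Independent binomial sampling gives 0.16, 0.14 and 0.10 at 50%, 65% and 75% women. For age, P(means differ by at least 0.25 SD) = 0.33.

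**Step 2: error rate at a given imbalance.** With d the difference between arms in the proportion of women, the test statistic for a null peak is shifted by

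z = d × b / √(2/30), where √(2/30) = 0.258.

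At d = 6/30 = 0.20 the shifts are 0.77, 1.55, 2.32 and 3.87 for b = 1, 2, 3 and 5. P(p<0.05) is then 12%, 34%, 64% and 97%. These values apply only to the less lucky randomisations of Step 1.

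**Step 3: average over all randomisations.** Weighting the Step 2 formula by the hypergeometric probabilities of d:

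| Women of 60 | b = 1 | b = 2 | b = 3 | b = 5 |
|---|---|---|---|---|
| 30 | 8% | 17% | 28% | 47% |
| 45 | 7% | 14% | 24% | 42% |

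**Step 4: check by another route.** If sex explains a share R² of a peak's variance, type I error after an arm-orthogonal surrogate is 2 × (1 − Φ(1.96 × √(1 − R²))). This gives 6.3%, 9.0%, 16.6%, 32.7% and 53.5% at R² = 0.10, 0.25, 0.50, 0.75 and 0.90. With half the patients women, R² = 0.25b²/(1 + 0.25b²), so b = 2 gives R² = 0.50 and 16.6%, in line with Step 3.

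**Step 5: effect at FDR 5%.** Simulation with 30 per arm, 70% women, 2,000 peaks, no treatment effect, 5% of peaks (100) sex-linked, 600 runs. The last three columns give P(p<0.05) for a sex-linked peak.

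| R² | Orthogonal surrogate: P(at least one sex-linked call) | Orthogonal surrogate: mean calls of 100 | Orthogonal surrogate | No adjustment | Explicit sex term |
|---|---|---|---|---|---|
| 0.25 | 0.020 | 0.0 | 0.088 | 0.050 | 0.049 |
| 0.50 | 0.095 | 0.3 | 0.153 | 0.043 | 0.050 |
| 0.90 | 0.573 | 27.0 | 0.539 | 0.048 | 0.053 |

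With the explicit sex term, P(at least one sex-linked call) was at most 0.002. A two-step SVA that re-estimates the surrogate on unresidualised data, so that it may correlate with arm, gave 0.050 to 0.053.

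**Step 6: before-after contrast.** With the same simulated patients at both times, type I error was 0.05 paired and 0.03 unpaired with a sex term, so sex does not inflate it.

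Batch follows the same algebra, but no figure is offered: the documents give neither batch sizes nor a rule for assigning samples to batches.

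**The case against.** **SVA need not be orthogonal to arm.** A reader might infer that SVA can never remove a chance imbalance. The documents do not support that: no algorithm is named, and the two-step version in Step 5 held about 5%. The independence phrase could also describe the sources targeted, which under randomisation are independent of assignment in expectation without being orthogonal in the sample; the vectors could be orthogonal only to one another. This stands as a limit. The plainer reading is still of surrogates built from what time and treatment leave unexplained and independent of both, so the risk is open.

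**Randomisation already covers imbalance.** It does for the unadjusted test, which keeps about 5%. Removing sex variance from the error term alone forfeits that protection.

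**The size can be overstated.** The 12%, 34%, 64% and 97% in Step 2 are conditional on a 20-point imbalance and refer to nominal p-values, whereas the plan selects at FDR 5%. They should not be read as the expected error rate.

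**Scope.** A reader might infer that any reported rehabilitation effect is exposed. The before-after contrast is not confounded by age or sex, because each patient appears at both times.

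**Other known factors may be intended.** The wording on known factors gives examples only, so more terms are possible. But age and sex are expressly placed among the unknown ones.

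**Cell mix.** A reader might also fault SVA for not removing a shift in PBMC composition that occurs with training. A shift caused by training is part of its effect, and adjusting for it changes the question.

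**Conclusion.** The point holds for the secondary cRHB vs RAGT chromatin contrast, on condition that the surrogates are orthogonal to arm. The plan's wording suggests this but does not settle it. Under that condition the stated method can do worse than no adjustment: the Step 3 averages run from 7-8% at a sex effect of 1 SD to 42-47% at 5 SD. After FDR selection the harm is slight for weakly or moderately linked peaks and substantial for strongly sex-linked ones. The sizes rest on the assumed sex ratio, effect sizes and share of sex-linked peaks, and on a Gaussian stand-in for edgeR. This is a cheap, worthwhile correction to a secondary analysis; it does not bear on the primary endpoint.

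**What to change.** 1. For the arm contrast, enter recorded age, sex and processing batch as known covariates in the edgeR design matrix. Estimate surrogate variables only for variation left after these terms, and name the SVA algorithm.
2. Add a patient block for the before-after comparison (none is now stated), and compare arms by the arm-by-time interaction. This also removes effects constant within a patient, including sex and baseline age, so those covariates are needed only where arms are compared at a single time point.
3. Reconcile the time labels. The molecular analysis uses T0 and T1, whereas section 3.1 and Table 1 make T1 baseline and T2 the end of training. Read literally, the stated arm comparison at T1 is a baseline comparison.

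The cost is a text change and a few degrees of freedom. Age and sex are already collected and batch needs only to be logged; no new samples are needed. Adjustment for cell fractions is not part of the required change.
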